### **1.7. Potential Risks**

In general, potential risks associated with the clinical use of REACT can be broadly divided into 3 categories: kidney biopsy, REACT product, and delivery into the recipient kidney. An assessment of potential risks associated with each of these steps is presented in this Section.

At this time, there are no specific warnings or precautions associated with the use of REACT. However, warnings and precautions for the renal biopsy and the percutaneous injection procedure must be considered with use of this product. The risks of renal biopsy have been well characterized in the 100 years that this procedure has been used and developed. Percutaneous needle instrumentation of the kidney has a shorter history.

The risks of renal biopsy and percutaneous needle kidney injection include:

1. Pain in flank / injection/biopsy site
2. Bleeding at injection/biopsy site which may occur around the kidney or anywhere along the needle track and which may be sufficient to entail clinically significant anemia, acute kidney injury (AKI), hematoma, and in the case of subcapsular bleeding, a “Page kidney” and acute hypertension
3. Surgical damage to the kidney from needle injury, as well as injuries of other structures that include connective tissues, bone, and intra-abdominal viscera

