## 8. SAFETY ASSESSMENTS AND MANAGEMENT

### 8.1. Adverse and Serious Adverse Events

#### 8.1.1. Definition of Adverse Events

An AE is the development of an undesirable medical condition (including abnormal laboratory findings) or the deterioration of a pre-existing medical condition following or during exposure to a study treatment, whether or not considered to have a causal relationship with study procedures or the investigational product. A pre-existing condition is a clinical condition (including a condition being treated) that is diagnosed before the subject signs the Informed Consent Form and is documented as part of the subject's medical history. Pre-existing conditions that are stable or unchanged should not be considered AEs.

The Investigator is responsible for ensuring that all AEs observed by the Investigator or reported by the subject that occur from the day of the biopsy procedure through 24 months after the final injection of REACT are monitored and recorded in the subject's medical record as well as the CRF provided by the Sponsor or its designee.

Treatment-emergent adverse events (TEAEs) are defined as any AE that started after the first injection of REACT or started prior to the first injection but increased in severity or frequency after the first injection of REACT.

Unscheduled visits may be performed at any time during the study as judged necessary by the Investigator to assess and conduct follow-up on AEs. Evaluations and procedures to be performed at unscheduled visits will be at the Investigator's discretion in consultation with the Sponsor and may be based on those listed in the Schedule of Events.

The Investigator's clinical judgment is used to determine whether a subject is to be removed from treatment due to an AE.

An AE is considered unexpected if it is not consistent in nature or severity with information contained in the current version of the **Investigator's Brochure** provided by the Sponsor.

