4.9 Analysis Periods

The following analysis periods will be defined as:

- Pre-Injection Period: from the start day of biopsy to the first REACT injection.
- Acute First Injection Period: from the first REACT injection to 1 month following the first REACT injection. The acute first injection period is a subset of the inter-injection period defined below.
- Inter-Injection Period: from the first REACT injection to either the second REACT injection or (if no such second injection was delivered) trial withdrawal or completion.
- Acute Second Injection Period: from the second REACT injection to 1 month following the second REACT injection. The acute second injection period is a subset of the post-second-injection period defined below.
- Post-Second Injection Period: from the second REACT injection to trial withdrawal or completion. This period will not apply to participants for whom only one REACT injection was delivered.
- Post-Injection Period: from the first REACT injection to trial withdrawal or completion. This period includes both the inter-injection and post-second injection periods.

[figure not shown]
If necessary, imputed dates will be used to determine the analysis period for adverse events.

Figure 1. Analysis Period Diagram for Subjects that Received Two Injections

Abbreviations: EOS = End of Study

Figure 2. Analysis Period Diagram for Subjects that Received One Injection

Abbreviations: EOS = End of Study

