6.3.4 Rate of Progression of Renal Disease

Using the IAS, the rate of progression of renal disease will be assessed graphically for eGFR as estimated by the 2009 CKD-EPI serum creatinine equation, serum creatinine, and 24 hour urine albumin, and 24 hour urine protein. For each subject a plot of the lab result versus time (in study days) will be displayed, showing vertical lines at biopsy date, 1st and 2nd injection, and the initiation of dialysis, if it is administered. Additionally, for eGFR, the rate of progression of renal disease will be assessed by estimating the annualized eGFR slope over time for each subject. Each subject will serve as his or her own control. The subject's previous medical history, which must include a minimum of 6 months of observation of renal function, will serve as the control for rate of progression of renal insufficiency. The historical eGFR measurements as well as all on study measurements taken prior to the first REACT injection will constitute the pre-injection period for this analysis.

The annualized rate of eGFR decline for the pre-injection, post-second injection, and post-injection periods will be estimated separately by linear mixed effects models. That is, separate models will be fit for each of the specific time periods: pre-injection, post-second injection, and post-injection periods. Each subject with a minimum of 3 observations during the period of interest will be modeled. The model will include unscheduled visits, and only the last measurement if there was a re-test on the same day.

For the pre-injection period, the linear mixed effects model will include eGFR as the dependent variable, and time (in years, derived as study day/365) as the independent variable. To account for between-subject variability in eGFR trajectories, random slopes and intercepts will be included. An unstructured covariance matrix will be used for the model. If the model cannot be fit with the unstructured covariance matrix, the following structure will be tried in the order listed below (decreasing number of parameters) until the one of them fit the model:

1. First-order autoregressive moving average (ARMA(1,1))
2. First-order autoregressive (AR(1))
3. Compound symmetry (CS)
4. Variance Components (VC)

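### The eGFR slope models have no washout after biopsy or injection, so a transient dip, if it occurs and is sampled, would bias both slopes in favour of REACT; a sensitivity run without the acute values is a cheap improvement

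*SAP*

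**What the plan says.** SAP 6.3.4 estimates annualized eGFR slopes from separate linear mixed models for three periods.

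- **Control line.** It uses historical values, and "all on study measurements taken prior to the first REACT injection will constitute the pre-injection period for this analysis". Post-biopsy values are its last points.
- **Treated lines.** SAP 4.9 defines "Post-Second Injection Period: from the second REACT injection to trial withdrawal or completion" and "Post-Injection Period: from the first REACT injection to trial withdrawal or completion". Neither has a washout.
- **Visits used.** "The model will include unscheduled visits, and only the last measurement if there was a re-test on the same day". Under Protocol 8.1.1, "Unscheduled visits may be performed at any time during the study as judged necessary by the Investigator to assess and conduct follow-up on AEs".
- **Minimum data.** "Each subject with a minimum of 3 observations during the period of interest will be modeled".
- **Exclusions by timing.** Only values after the start of dialysis are removed (SAP 6.2). SAP 4.4 plans no analysis windows.

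SAP 4.9 also defines a one-month acute period after each injection. The adverse event summaries use it (SAP 7.2.5); the slope models do not. Protocol 1.7 lists, among the risks of biopsy and needle injection, bleeding "sufficient to entail clinically significant anemia, acute kidney injury (AKI), hematoma". No expected size or duration of an eGFR dip is given.

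**The concern.** A straight line is sensitive to its end points. A low value at the end of the control line makes the historical decline look steeper. A low value at the start of a treated line, followed by recovery, makes the later decline look slower. The first can follow a biopsy and the second an injection, and both point towards benefit.

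Protocol section 2 proposes that REACT will reduce the rate of eGFR decline, with each subject's own history as comparator. There is no concurrent control group to carry the same artefact. The slope table prints only the number of subjects, the slope and its standard error, so it cannot separate slower decline from recovery after a procedure. Subjects enter at eGFR 14 to 20 mL/min/1.73m², where a dip of a few units is a large share of function.

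**Working it through.** The plan states no slope, effect size or power, so there is no figure to reproduce. The check asks how far an assumed dip moves a least-squares slope on the protocol visit times. The answer does not depend on the true slope.

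**Assumed dip.** It is d at Day 1, d/2 at Day 14 and zero by Day 28, linear in between.

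**Formula.** Bias = Σ(tᵢ − t̄)·δᵢ / Sxx, where δᵢ is the negative dip at visit i, t is in years and Sxx = Σ(tᵢ − t̄)².

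**Post-second line.** Visits: Days 1, 14, 28 and Months 2, 3, 6, 9, 12, 15, 18, 21, 24 (12 visits; Protocol 6.5 and the Table 2 column headings). t̄ = 0.774, Sxx = 5.60.

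- Bias = d × [(0.774 − 0.003) + 0.5 × (0.774 − 0.038)] / 5.60 = 0.203d. For d = 1, 2, 3 this is +0.20, +0.41, +0.61 per year.
- Without a Day 1 value (11 visits, t̄ = 0.844, Sxx = 4.95), d = 2: (0.844 − 0.038)/4.95 = +0.16.
- Follow-up ending at Month 12, for example because of dialysis (8 visits, t̄ = 0.348, Sxx = 0.941), d = 2: 2 × [0.345 + 0.5 × 0.310]/0.941 = +1.06.
- Sampling only at the Protocol 9.4 times, which start at 1 month: 0, because this dip is gone by Day 28. With exponential recovery instead (dips of 1 to 3, half-lives of 7 to 30 days) the same grid gives +0.01 to +0.51.

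**Control line.** Days relative to first injection: biopsy −30 (Protocol 6.2, about one month), pre-biopsy visit −32, pre-injection visit −12 (Protocol 6.3, 10 to 14 days before). Three historical values are assumed, the last at screening on day −90. The pre-injection visit is 18 days after biopsy, so the dip there is 2 × 0.357 = 0.714 for d = 2.

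- 6-month history (t̄ = day −117.6, Sxx = 0.355): −0.714 × (105.6/365)/0.355 = −0.58.
- 24-month history (t̄ = day −281.8, Sxx = 3.69): −0.714 × (269.8/365)/3.69 = −0.14.
- With the optional Day 1 post-biopsy value, 6-month history (Sxx = 0.404): −(2 × 0.202 + 0.714 × 0.249)/0.404 = −1.44. With a 24-month history (Sxx = 4.09): −(2 × 0.577 + 0.714 × 0.624)/4.09 = −0.39.

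Other placements of the screening and historical values move the 6-month figures to between about −0.4 and −0.6 (without Day 1) or −1.0 and −1.5 (with it).

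**Whole post-injection line** (19 visits, second injection at day 183). A dip of 2 after each injection biases the slope by +0.33. A lasting loss of 1 mL/min/1.73m² at the second injection changes it by −0.44.

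**Group level.** These are per-subject figures. If a share p of subjects dips, the mean shifts by roughly p times the bias: 3 of 10 with d = 2 gives 0.3 × 0.41 = +0.12 post-second.

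**Mixed-model check.** The simulation had no treatment effect, 10 subjects and 100 replicates. It assumed a true slope of −5 per year (SD 2), residual SD 1.2, and a dip of 2 with a 14-day half-life in every subject.

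| Values used | Control slope | Post-second slope | Apparent gain |
|---|---|---|---|
| All, as planned | −5.09 | −4.49 | +0.60 |
| Acute values dropped | −4.95 | −4.96 | −0.01 |

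With no dip, the gain as planned is +0.02.

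**The case against.** **The control half is limited.** The post-biopsy Day 1 visit is held only after a safety event (notes to Protocol Tables 1 and 2). Acute kidney injury or rapid decline in the three months before injection is exclusionary (Protocol 5.2, criterion 14). Subjects whose post-biopsy events raise the injection risk are not treated (Protocol 7.5.1), and the slopes use only injected subjects. Much marked post-biopsy injury would never reach the control line. This stands, so the scheduled-visit figures are the ones to rely on.

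**Early eGFR sampling is inferred.** The post-injection cells of Table 2 are not legible in the copy reviewed. Sampling on Days 1 and 14 is read from the column headings, and Protocol 9.4 lists eGFR only from one month. This stands, and is why the treated-side range includes zero.

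**The injury is not hidden.** A reader might infer that procedural injury would be reported only as an efficacy signal. The documents do not support that. SAP 6.3.4 plots each subject's eGFR with lines at biopsy and both injections. SAP 6.2 summarizes renal laboratory values by visit, SAP 7.3 gives shift tables by period, and SAP 7.2.5 reports events by relationship to biopsy, product and injection procedure. Two gaps remain. Laboratory tables omit unscheduled results that the slope model keeps, and Protocol 8.3 does not require every clinically significant laboratory change to be reported as an adverse event.

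**Lasting loss behaves differently.** A reader might also infer that any lasting drop at injection disappears into an intercept. That is true only of the post-second line. The whole post-injection line runs through the second injection, and a lasting loss there steepens it, against REACT.

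**No test is planned.** The slopes are exploratory, in up to 10 subjects, and no slope difference is tabulated. No type I error rate is affected.

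**Conclusion.** The structure is in the text and the direction of bias is certain for transient injury that is sampled. Its size is not documented; every figure rests on an assumed dip, duration and sampling pattern.

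For a dip of 2 mL/min/1.73m² that clears by Day 28:

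- The post-second slope is biased by about +0.4 per year. It is +0.16 without a Day 1 sample, 0 on the Protocol 9.4 times, and about +1.1 if follow-up stops at 12 months.
- The control slope is biased by about −0.1 (24-month history) to −0.55 (6-month history) on scheduled visits. It is about −0.4 to −1.4 where the safety-triggered Day 1 value exists.

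The documents do not show that such dips occur, so the planned slopes cannot be called biased as they stand. They leave recovery from a procedure and slower decline indistinguishable in the slope table. That makes this a cheap improvement to interpretation.

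**What to change.** Keep the planned slopes and add to SAP 6.3.4 a pre-specified sensitivity run:

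1. Drop eGFR between biopsy and first injection from the control line.
2. Drop the SAP 4.9 acute month after each injection from the post-second and post-injection lines.
3. Print both sets of slopes side by side, with the number of subjects still meeting the three-observation minimum.
4. Report the acute change as the lowest value in the acute month, and as the Day 28 value, each minus the last value before that injection. Day 28 alone would miss a dip that has already recovered. The lowest of several values is pulled down by noise, so the two should be read together.

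The cost is one more model run and one table. The measurement-error standard error of a subject's slope rises by about 28% post-second (√(5.60/3.44) = 1.28, from 12 visits to 9). It rises by about 20% for the post-injection line (19 visits to 13) and by roughly 10 to 20% for the control line. A few subjects with short follow-up may fall below three observations. Slow recovery is not fully removed: with exponential recovery (dips of 1 to 3, half-lives of 7 to 30 days) the post-second bias after the change is 0.00 to +0.28 per year.

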#### 1.6.4. Serum Creatinine

[figure not shown]
Pre-treatment levels of serum creatinine (sCr) were generally elevated in this cohort, which would be expected from subjects with T2DM and moderate to severe renal insufficiency (Stage 3b/4 of

CKD). The annual rate of change for sCr, before and after REACT treatment, is presented for each subject in Table 8. All subjects demonstrated a reduction in their individual rate of increase for sCr following REACT treatment compared to the rate of sCr increase that had been observed before REACT treatment.

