## 2. PHASE II TRIAL OBJECTIVES AND PURPOSE

ProKidney is currently developing a regenerative cell-based product, Renal Autologous Cell Therapy (REACT), with the aim of improving renal function in subjects who have CKD and T2DM. Therapeutic intervention with REACT is intended to delay the need for renal replacement therapy (dialysis or transplant) which, based on the current standard-of-care, is inevitable for patients with end-stage CKD. The purpose of the present study is to compare the safety and efficacy of up to 2 injections of REACT given 6 months (+4 weeks) apart (maximum). Each subject's annual rate of renal decline, based on adequate historical clinical data from 24 months prior to the Screening Visit, will serve as a comparator to monitor the rate of progression of renal insufficiency.

We propose that REACT treatment will reduce the rate (slope) of eGFR decline and improve renal function over the 24-month period following the last REACT injection.

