2.2.3 Exploratory Endpoints

Exploratory endpoints include:

- 1) Clinical diagnostic and laboratory assessments of renal structure and function (including eGFR, serum creatinine, and proteinuria) to assess changes in the rate of progression of renal disease.

- a. Clinical diagnostic assessments of renal structure and function consist of results from renal ultrasounds (cortical thickness, length, and volume by treated/untreated kidney) and renal scintigraphy (differential renal function by treated/untreated kidney).
- b. Laboratory assessments considered exploratory endpoints include: eGFR as estimated by three Chronic Kidney Disease Epidemiology Collaboration (CKD-EPI) equations [2009 CKD-EPI serum creatinine equation, 2012 CKD-EPI cystatin C equation, and 2012 CKD-EPI serum creatinine-cystatin C equation], serum creatinine, 24 hour urine albumin, and 24 hour urine protein.

2) Patient-reported outcomes from Kidney Disease Quality of Life (KDQOL) and EQ-5D-5L surveys obtained at baseline (i.e., before REACT injection) through 24 months after the last REACT injection.

3) Time to dialysis

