For the post-secondary period, and separately for the post-injection period as a whole, linear mixed effects models will be fit including eGFR as the dependent variable, time (in years, derived as study day/365) as the independent variable, and baseline eGFR as a covariate. To account for between-subject variability in eGFR trajectories, random slopes and intercepts will be included. An unstructured covariance matrix will be used for the model. If the model cannot be fit with the unstructured covariance matrix, the same procedure as for the pre-injection period will be followed.

A table will be presented to display the following for each time period of interest: number of subjects included in the model, the estimated slope for the time variable, and the associated standard error. If no model can be fit, the table will simply display a message "Model did not converge."

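### SAP 6.3.4 makes each subject his or her own control but never summarises the within-subject change in eGFR slope, and its table cannot supply a standard error for that change

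*SAP*

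**What the plan says.** The exploratory endpoint in SAP 2.2.3 is "to assess changes in the rate of progression of renal disease". Protocol section 2 states the expectation behind it: "We propose that REACT treatment will reduce the rate (slope) of eGFR decline". SAP 6.3.4 makes each subject his or her own control. The control is the medical history, "which must include a minimum of 6 months of observation of renal function", together with on-study values before the first injection. The section also says that an annualized eGFR slope will be estimated for each subject.

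The modelling text then says that "separate models will be fit for each of the specific time periods: pre-injection, post-second injection, and post-injection periods". Entry is decided period by period: "Each subject with a minimum of 3 observations during the period of interest will be modeled". The post-period models add baseline eGFR as a covariate and the pre-injection model does not. The table shows, for each period, "number of subjects included in the model, the estimated slope for the time variable, and the associated standard error". On the post-second-injection period, SAP 4.9 adds: "This period will not apply to participants for whom only one REACT injection was delivered".

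Subject-level plots (SAP 6.3.4), laboratory listings (7.3) and change from baseline in eGFR (6.2) are also planned. No section defines a difference in slope between periods, for a subject or on average. SAP section 10, which lists departures from the protocol, does not mention the point.

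**The concern.** The quantity of interest is a change in slope within a subject. The plan produces three unlinked average slopes. A reader who wants the change must subtract two of them, and meets two problems.

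First, the uncertainty of that difference depends on how strongly a subject's slope before injection correlates with the slope after it, and none of the three models estimates this. Second, the models need not contain the same subjects. A subject who received one injection is in the pre-injection model but not in the post-second-injection model. Protocol 3.2.5.1 lists rapid renal deterioration among the reasons to withhold the second injection. Protocol 5.1 re-checks inclusion criteria, including eGFR 14 to 20, before each injection. The subjects missing from the post-second-injection slope may therefore be those whose eGFR fell most.

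At stake is the only slope evidence that the study will give for the protocol's proposition about eGFR decline.

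**Working it through.** The documents give no SD, correlation, power or target effect, so there is no planned figure to reproduce. All inputs below are assumptions except the visit schedule and the maximum of 10 subjects. Slopes are in mL/min/1.73 m² per year.

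**1. What the table would print.** Assume n = 10, residual SD s = 1.5 and between-subject slope SD 2 in each period. Assume 6 pre-injection values: three historical, screening, pre-biopsy and pre-injection. Assume 18 post-injection values: days 14 and 28, months 2 to 5 and the visit before the second injection; then days 14 and 28 and months 2, 3, 6, 9, 12, 15, 18, 21 and 24 after it. With Sxx the sum of squared deviations of the visit times, the error variance of one subject's slope is s²/Sxx:

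- post-injection: 2.25/10.24 = 0.22 (SE 0.47)
- pre-injection, 2-year history: 2.25/3.26 = 0.69
- pre-injection, about 9 months in all: about 6.98 (Sxx about 0.32)

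With the 2-year history the printed SEs are √((4 + 0.69)/10) = 0.685 and √((4 + 0.22)/10) = 0.650. Neither contains the pre/post correlation ρ. Combined as if independent they give √(0.469 + 0.422) = 0.94.

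**2. What the change needs.** SE(change) = √{[2·2²·(1 − ρ) + s²/Sxx_pre + s²/Sxx_post]/n}. With the 2-year history this is √{[8(1 − ρ) + 0.91]/10}, and with about 9 months √{[8(1 − ρ) + 7.20]/10}.

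| ρ | Paired SE, 2-year | 0.94 combined ÷ paired | Paired SE, 9-month | 1.23 combined ÷ paired |
|---|---|---|---|---|
| -0.5 | 1.14 | 0.83 | 1.39 | 0.89 |
| 0 | 0.94 | 1.00 | 1.23 | 1.00 |
| 0.5 | 0.70 | 1.35 | 1.06 | 1.17 |
| 0.8 | 0.50 | 1.88 | 0.94 | 1.31 |

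The ratios use unrounded SEs. Identical printed output is thus compatible with a true SE anywhere from 0.50 to 1.14 (2-year history).

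**3. Who is in each model.** Take a mean slope of -4 in both periods, so no treatment effect, and eGFR spread evenly over 14 to 20 at first injection. Six months later the average fall is 4 × 0.5 = 2, so the range is about 12 to 18 and roughly 2/6 = 33% lie below 14. A simulation that adds slope variation and measurement error, and withholds the second injection when the value before it is outside 14 to 20, leaves out about 35% to 40% of subjects. The post-second-injection slope then exceeds the all-subject pre-injection slope by about +0.3 to +0.5. Restricting the pre-injection slope to the same subjects usually lowers this (in one setting from 0.49 to 0.10), but in another it rose from 0.30 to 0.36. The whole-post-injection minus pre-injection contrast ranged from -0.22 to +0.01. If withholding is unrelated to eGFR, the post-second-injection bias is zero.

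**4. Whether a paired interval is sound.** Protocol 7.3.1 sends study samples to a central laboratory, while historical values come from site laboratories. An assumed +1 step between the three historical and the three on-study pre-injection values moves the pre-injection slope by about +0.5 (2-year) or +1.7 (9-month). In simulation, coverage of a paired 95% t interval then falls to 0.91 and 0.86 (2-year; ρ = 0.5 and 0.8), or 0.72 and 0.65 (9-month). Without such a step it is about 0.95.

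**The case against.** The strongest reply is that the plan already goes part of the way. It promises a slope for each subject, its models carry random slopes, it plots every subject, and it prints n per model. The study is descriptive, with at most 10 subjects and no hypothesis tests, and readers can subtract two slopes. Much of this is right. A reader might infer that no subject-level slopes are planned; SAP 6.3.4 says otherwise. What is missing is a table of them and a summary of the change. Having no tests does not settle the matter, since an estimate with an interval is descriptive and the plan already prints standard errors for other quantities.

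A reader might also infer that the slope analysis as a whole favours REACT. The documents do not support that. The selection effect arises only if withholding follows decline. It concerns the post-second-injection slope, and the whole post-injection slope in the injection analysis set is already planned.

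Nor can it be said that the combined standard error is always too large: the direction depends on a correlation that the documents do not give. A positive value, for which combining errs on the cautious side, may be the more natural guess, and nothing in the documents points to a negative one.

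Finally, a paired interval is not a clean cure. The change of laboratory can shift it, and that same shift already affects the planned pre-injection slope.

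**Conclusion.** The point holds as a modest improvement worth making. SAP 6.3.4 does not summarise the change that its endpoint names, and the planned table cannot give that change a valid standard error. Under the stated assumptions, the standard error a reader would construct is 0.83 to 1.88 times the paired one with a 2-year history, and 0.89 to 1.31 times with about 9 months. Separately, the post-second-injection slope can look better by about +0.3 to +0.5 per year with no treatment effect, if the eGFR range is applied again before the second injection as modelled here. These sizes rest on assumed SDs, correlations, visit spacing and withholding rule. That the change and its covariance are absent does not. The endpoint is exploratory, and nothing here touches the primary safety conclusion or calls for a hypothesis test.

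**What to change.** Keep the planned models and add one table to SAP 6.3.4.

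- For subjects in the injection analysis set with at least 3 eGFR values in both periods, list the pre-injection slope, the whole post-injection slope and their difference. Give the mean difference with a t-based 95% CI, labelled descriptive. Protocol 1.6.4 sets a precedent in the Phase 1 data: "The annual rate of change for sCr, before and after REACT treatment, is presented for each subject in Table 8".
- Show the post-second-injection slope beside the pre-injection slope of the same subjects. List one-injection and excluded subjects with reasons, including early dialysis, since SAP 6.2 removes values after dialysis starts. Note that matching does not remove selection on outcome.
- State the laboratory source of each value; Protocol section 6 also allows local laboratories during follow-up. Caveat the interval, or repeat it on same-laboratory values where the local re-analysis foreseen in Protocol 7.3.1 exists.

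The cost is SAP wording and one small table, with no new data. There are three downsides. Equal weighting is noisy when follow-up is short: a subject with three post-injection values ending at 2 months has a slope SE of 16.1. At ρ = 0.5 with a 2-year history this raises the SE of the mean change from 0.70 to √[(9 × 4.91 + 4 + 0.69 + 16.1²)/100] = 1.76. Complete-case selection remains. The interval is wide: over the ρ range above, the 95% half-width with 10 subjects is 2.262 × SE, or 1.13 to 2.57.
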